1.2.2. Clinical Studies

1.2.2.1. Clinical Pharmacology Studies

The pharmacokinetics (PK) of MPA following a single subcutaneous injection of undiluted and saline diluted 120 mg TV-46046 has been evaluated in a single Phase 1 study which included 12 healthy subjects (Study TV46046-WH-10075). All subjects, except 1 in the undiluted TV-46046 group, had serum MPA levels greater than 0.20 ng/mL 24 hours after treatment initiation. Maximum observed serum drug concentration (C_{max}) in the undiluted TV-46046 group and the

saline-diluted TV-46046 group were 0.53 ng/mL and 0.97 ng/mL, respectively. Areas under the concentration curve (AUC_{0-∞}) of the undiluted TV-46046 group and the saline-diluted TV-46046 group were 94.56 days*ng/mL and 114.13 days*ng/mL, respectively. All evaluable subjects in the undiluted

TV-46046 group and all except 1 subject in the saline-diluted TV-46046 group had serum MPA concentrations exceeding 0.10 ng/mL on Day 182. The apparent half-lives of the undiluted TV-46046 group and the saline-diluted TV-46046 group were 82.87 and 42.34 days, respectively.

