4.3. Handling of Withdrawals and Missing Data

4.3.1. Discontinuation and Missing Data

Subjects who are discontinued from the study after being randomized will not be replaced. All available data up to the time of discontinuation will be included in relevant analyses. Except as noted in Section 4.3.2, missing data will not be estimated or imputed.

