10.5. Noncompartmental Analysis

The following protocol-specified pharmacokinetic parameters will be estimated based on NCA: C_{max} , T_{max} , C_{91} , C_{182} , C_{210} , AUC_{0-182} , AUC_{0-210} , $AUC_{0-\infty}$, and the apparent terminal half-life (computed as $\log_e[2]/\lambda$). Additional estimates will include AUC through day of last quantifiable sample (AUC_{0-last}), and time above 0.2 ng/mL (extrapolated to infinity). Detailed rules used to estimate these parameters, and conditions that must be met to report the estimate, are as follows:

- C_{max} will be based on the maximum observed MPA concentration for subjects who a) provide at least one MPA result after their highest observed concentration and b) do not use a concomitant medication known to impact the pharmacokinetics of MPA before the occurrence of C_{max} . Values of C_{max} for subjects who fail to meet these two criteria will be considered non-evaluable and excluded from the primary pharmacokinetic analysis.
- T_{max} will be based on the day (rounded to the first decimal place) when C_{max} was initially observed. Values of T_{max} for subjects who's C_{max} is non-evaluable (per above) will be excluded from primary analyses.
- C_{91} , C_{182} , and C_{210} will be based on evaluable results in the corresponding pre-defined visit windows ([Table 2](#)). If a subject has more than one MPA result in the same visit window, then the value closest to the nominal time will be used.
- λ will be estimated as minus the slope of the terminal phase, based on the last three or more log-transformed MPA concentrations after C_{max} but on or before T_{last} , regressed on time. The specific number of time points used to compute λ will be determined based on the unweighted regression with largest adjusted R^2 . If the estimated slope is not negative, or if fewer than three time points are available for estimating λ , then no value will be reported.
- Partial AUC values will be computed using the ‘linear up log down’ rule as implemented in Phoenix WinNonLin (version 8.3 or higher). No AUC value will be reported if C_{max} was not estimable per above.
- $AUC_{0-\infty}$ will be computed as $AUC_{0-last} + C_{last}/\lambda$, where C_{last} is the last quantifiable drug concentration measurement

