- Time at or above 0.2 ng/mL will be computed using linear up log down interpolation if the 0.2 ng/ml threshold is crossed between two sampling time points, and log down interpolation when extrapolating to infinity.

Except for $t_{1/2}$, the primary measure of central tendency and dispersion for each pharmacokinetic parameter estimate will be the GM and geometric %CV; for $t_{1/2}$, the harmonic mean and %CV based on a jackknife estimate of SD will be reported. Additional summaries will include mean, SD, SE, median, minimum, maximum, and 95% CIs for means. Measures of AUC, T_{max} , and $t_{1/2}$ will be reported to one decimal place. Drug concentration parameter estimates (e.g. C_{max} and

Statistical Analysis Plan Version 5.0

Pharmacokinetics Study–Healthy Subjects

Study TV46046-WH-10159

C_{182}) will be summarized using the same number of decimal places as the original data. Subject listings will include each of the above parameter estimates as well as the percent of AUC extrapolated to infinity.

[figure not shown]

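### SAP 10.5 sets no limit on the extrapolated share of AUC0-∞, so a woman last sampled at about Week 8 to 13 can enter the geometric mean and GM ratio with a poorly supported value

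*SAP*

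**What the plan says.** SAP 10.5 gives an estimation rule and reporting conditions for each parameter.

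- **Any AUC:** "No AUC value will be reported if C_{max} was not estimable per above". Cmax is evaluable if at least one result follows the peak and no interacting medication was used before it.
- **Terminal slope λ:** "If the estimated slope is not negative, or if fewer than three time points are available for estimating λ , then no value will be reported". On which points to use: "The specific number of time points used to compute λ will be determined based on the unweighted regression" with the largest adjusted R². No minimum R², time span or length of follow-up is set.
- **AUC0-∞:** AUC to the last quantifiable sample plus Clast/λ.
- **Time at or above 0.2 ng/mL:** interpolated between samples, "and log down interpolation when extrapolating to infinity".
- **Extrapolated share:** "Subject listings will include each of the above parameter estimates as well as the percent of AUC extrapolated to infinity". No action depends on it.

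On women who leave early, SAP 4.3.1 says "All available data up to the time of discontinuation will be included in relevant analyses"; they are not replaced. AUC0-∞ is a primary endpoint (SAP 1.1.2). It is summarised by the geometric mean (10.5) and compared with the reference by GM ratio and 90% CI (10.6).

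**The concern.** The reporting conditions test whether a slope can be calculated, not whether the woman was followed long enough for it to be the terminal slope. Protocol 1.2.2.1 says of the earlier 120 mg study: "The apparent half-lives of the undiluted TV-46046 group and the saline-diluted TV-46046 group were 82.87 and 42.34 days, respectively". Against 82.87 days, Week 8 is 0.7 half-lives and Week 13 is 1.1. If release from the depot keeps concentrations roughly level for the first weeks, the last few points of an early leaver may lie on that plateau. A falsely shallow slope makes Clast/λ very large, so the error leans upward.

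At stake are the AUC0-∞ geometric mean, its geometric CV and the GM ratio in arms of about 15. Early leaving is not the only route. The interim review requires only 80% of treated women to have had the opportunity for 7.5 months of follow-up (SAP 2.6.1), so up to 12 of 60 may have less.

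**Working it through.** The plan states no extrapolation figure, so there is nothing to reproduce.

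**Inputs.** From Protocol 1.2.2.1 (undiluted / diluted groups): half-life 82.87 / 42.34 days, Cmax 0.53 / 0.97 ng/mL, AUC0-∞ 94.56 / 114.13 day·ng/mL. Arm size is 15 (SAP 2.5). The 32 MPA sampling times come from Protocol Table 1.

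**1. Extrapolated share under single exponential decline**, 2^(−t/t½):

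| Last sample | t½ 82.87 d | t½ 42.34 d |
|---|---|---|
| Day 56 (Week 8) | 63% | 40% |
| Day 91 (Week 13) | 47% | 23% |
| Day 224 (Week 32) | 15% | 3% |
| Day 364 (Week 52) | 5% | 0.3% |

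The share falls to one half at one half-life: about day 83 or day 42.

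**2. Is there a plateau?** For pure exponential decay, AUC/Cmax equals t½/ln 2.
- Undiluted: 94.56/0.53 = 178 days against 82.87/0.693 = 120, an excess of about 59 days.
- Diluted: 114.13/0.97 = 118 days against 42.34/0.693 = 61, an excess of about 57 days.

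Both suggest roughly eight weeks before decline. These are group summaries from a 12-subject study, so this is indicative only.

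**3. Simulation of the SAP 10.5 rules.** Linear-up log-down AUC; λ by largest adjusted R² on at least three post-Cmax points; negative slope required. Assumed: a plateau-then-decline profile at the 82.87-day half-life, between-subject SD of log 0.25–0.30, residual error 10–20%. Among women who get a value:

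| Last sample | Get a value | Median share extrapolated | Estimated/true, 5th to 95th percentile |
|---|---|---|---|
| Week 8 | about 40–50% | 65–83% | 0.5–0.8 to about 5–10 |
| Week 13 | 74–88% | 44–54% | 0.6–0.7 to 2.2–3.1 |
| Week 32 | not tabulated | 15–16% | 0.85–0.91 to 1.08–1.15 |
| Week 52 | not tabulated | 5% | 0.93–0.96 to 1.04–1.10 |

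Other assumed profile shapes put the proportion of Week 8 leavers who get a value anywhere from 1% to 61%. At the 42.34-day half-life the problem is milder: for a last sample at day 84 the median share is 38% and the 95th-percentile ratio is 1.5–2.0.

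**4. Effect on a 15-woman geometric mean.** One value wrong by a factor f shifts it by f^(1/15) − 1.
- f = 2: +4.7%; f = 3: +7.6%; f = 5: +11.3%; f = 8: +14.9%; f = 10: +16.6%.
- At the simulated Week 8 medians (f = 1.2 to 1.7): +1.2% to +3.6%.
- At the Week 13 95th percentiles (f = 2.2 to 3.1): +5.4% to +7.8%.
- At the Week 52 95th percentile (f = 1.10): +0.6%.

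Across the alternative shapes, the 5th to 95th percentile for one Week 8 leaver ran from about −4% to +24%. The top end comes from the shape in which only about 1% of such women get a value.

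**5. Effect of a 20% limit.** In the simulation, at final analysis it removes about 2% of Week 52 completers and nearly all values ending by Week 8. For women last sampled at about Week 32 with the 82.87-day half-life, it removes roughly 30%, although their estimates are within about 15% of truth. The true geometric mean of those retained is then 6–9% too low, because slow-release women have the larger shares.

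**The case against.** - **The SAP's own rules screen out many bad values.** True: the slope and three-point conditions withhold about half or more of Week 8 values in the main simulation. They withhold few at Week 13.
- **Few women may leave that early.** Protocol 9.1 aims for at least 54 women completing 32 weeks and allows extra enrolment. The documents give no early dropout rate, so the number affected is unknown and may be zero or one per arm.
- **Other safeguards exist.** AUC0-last is planned, and medians and ranges are reported. Blinded review before the first interim covers possible outliers (SAP 2.3), and a bootstrap is available (10.6). These help a reader, but SAP 2.3 gives no criterion, the bootstrap changes only the interval, and the 10.7 sensitivity analysis removes nothing.
- **A limit may exist out of sight.** A figure near the end of 10.5 is not shown, 10.8 is redacted, and the imputation rules for partial-AUC end-times cited in 4.3.2 and 10.7 are not readable. This cannot be ruled out.
- **Exclusion can itself bias.** This stands for data ending near Week 32 and shapes the fix.

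A reader might infer that dose selection is at risk. The documents do not support that. The criteria in Protocol 1.4.2 are the 6-month trough against the reference 3-month trough and the risk of return to ovulation; neither uses λ. Nor does time above 0.2 ng/mL enter a GM ratio: it is an additional estimate in 10.5 and is absent from the 10.6 list.

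**Conclusion.** The gap is real in the readable text and worth closing, but its reach is limited. It affects AUC0-∞, and extrapolated time above 0.2 ng/mL, for women whose sampling stops at about Week 8 to 13. Completers are estimated well. One affected woman usually moves an arm's geometric mean by a few percent; about 10–15% is an upper-tail result, not a typical one. It would also be wrong to read every early leaver's value as mostly extrapolated: at the 82.87-day half-life that stops being true at about Week 13, and earlier at 42.34 days. Cmax, C91, C182, C210 and the C182-to-C91 trough comparison do not depend on this extrapolation.

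The sizes rest on assumed profile shapes and variances matched to summaries from one small study. The 20% limit is a proposal, not a figure from the documents.

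**What to change.** In SAP 10.5 and 10.6:

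1. Flag every AUC0-∞ with more than 20% extrapolated and give counts by arm.
2. At the final analysis, report the AUC0-∞ summary and GM ratio both without flagged values and with all values, next to the planned AUC0-last.
3. At the 7.5-month interim, flag and show both versions, but do not exclude flagged values from the main summary, because a cap there selectively removes slow-release women and biases exposure downward. SAP Section 12 says that the Version 5.0 changes were not applied to the interim analysis, so this step may concern only a further interim of the kind SAP 2.6.1 allows.
4. Flag time above 0.2 ng/mL when the crossing lies beyond Tlast, but do not drop it, since that would remove the longest durations. Show it as at least Tlast beside the extrapolated value.

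The cost is a few sentences and a second set of AUC0-∞ estimates, using a percentage already computed. About 2% of completers' values would be absent from one of the two versions.

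### SAP 10.5 makes the geometric mean the primary summary of time at or above 0.2 ng/mL, a duration that is zero for any woman who never reaches that level (minor)

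*SAP*

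**What the plan says.** SAP 10.5 lists the protocol's noncompartmental parameters and adds two more, AUC to the last quantifiable sample "and time above 0.2 ng/mL (extrapolated to infinity"). For the duration it prescribes "linear up log down interpolation if the 0.2 ng/ml threshold is crossed between two sampling time points", and log-down extrapolation beyond the last sample. It gives no rule for a profile that stays below 0.2 ng/mL throughout.

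The summary rule follows: "the primary measure of central tendency and dispersion for each pharmacokinetic parameter estimate will be the GM and geometric %CV". The only exception is half-life, for which "the harmonic mean and %CV based on a jackknife estimate of SD will be reported". The same paragraph continues: "Additional summaries will include mean, SD, SE, median, minimum, maximum, and 95% CIs for means". Subject listings of each estimate are also planned.

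The imputation rules in SAP 4.3.2 and 10.2 cover MPA concentrations, other laboratory values below the LLOQ and partial dates. None covers a duration. SAP 10.6 does not list time above 0.2 ng/mL among the GM ratios, and SAP 1.1.2 does not list it among the primary endpoints.

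**The concern.** A GM needs every value to be positive. A duration above a threshold can be exactly 0, and then neither its logarithm nor the geometric %CV exists. The rule suits the peak and the AUCs, which are positive for any woman with measurable drug, and it suits visit concentrations, where SAP 10.2 replaces post-dose values below the LLOQ by half the LLOQ. It was extended to this duration without a matching provision.

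The woman affected is the one with the least exposure. If her value is left out because it cannot be logged, the arm's headline duration goes up and its headline variability goes down. The trial is meant to inform selection of a dose for 6-monthly injection, and this estimate is expressed directly as a duration, so its headline should be defined for every evaluable woman.

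**Working it through.** The documents give no figure for this summary, so there is none to reproduce. The check has three parts.

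**1. Can the value be zero under the SAP's rule?** Apply linear-up log-down crossing to two invented profiles sampled on Days 0, 1, 2, 3, 5 and 7.

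- Concentrations 0, 0.12, 0.17, 0.21, 0.18, 0.17: upward crossing at 2 + (0.20 − 0.17)/(0.21 − 0.17) = 2.75 days, so 0.25 day before the Day 3 sample. After it, 2 × ln(0.21/0.20)/ln(0.21/0.18) = 0.63 day. Total 0.88 day.
- The same profile with a peak of 0.19: no crossing, total 0 days.

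**2. What does one zero do to the summary?** Use GM = exp(mean of ln x) and geometric %CV = 100 × √(exp(variance of ln x) − 1). The illustrative arm is 15 evenly spaced log-normal quantiles with an assumed GM of 200 days and CV of 40%. These are not trial data.

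| Lowest woman | GM (days) | Geometric %CV | Median (days) |
|---|---|---|---|
| own value (98.7 days) | 200.0 | 39.7 | 200.0 |
| 0 days, kept | 0 or undefined | undefined | 200.0 |
| 0 days, left out (n = 14) | 210.4 | 35.1 | 206.7 |

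Leaving her out moves the GM up by 5% (210.4/200.0) and the %CV down. With her zero kept, the median is defined and stays at 200.0.

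**3. How likely is a zero?** Inputs: 15 women per group (SAP 2.5); earlier 120 mg peaks of 0.53 ng/mL undiluted and 0.97 ng/mL saline-diluted (Protocol 1.2.2.1). The protocol does not say what type of average these are; I take them as GMs. The between-woman CV is not given, so I assume 30% to 60%. With log-normal peaks, σ = √ln(1 + CV²), p = Φ[ln(0.2/GM)/σ], and the chance of at least one zero in 15 is 1 − (1 − p)^15.

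| CV | σ | p at 0.53 | At least one in 15, at 0.53 | At least one in 15, at 0.97 |
|---|---|---|---|---|
| 30% | 0.294 | 0.0005 | 0.7% | below 0.1% |
| 40% | 0.385 | 0.0057 | 8% | below 0.1% |
| 50% | 0.472 | 0.0196 | 26% | 0.6% |
| 60% | 0.555 | 0.0394 | 45% | 3% |

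For example, at CV 50%: ln(0.2/0.53) = −0.975; −0.975/0.472 = −2.06; p = 0.0196; 1 − 0.9804^15 = 0.26.

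**The case against.** The case for leaving the text alone is substantial.

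- **Role of the estimate.** It is an additional estimate. The dose-range criteria in Protocol 1.4.2 are a 6-month trough comparable with the reference product's 3-month trough and a low risk of ovulation within 7 months. Neither uses this duration. This stands and limits the weight.
- **What is already reported.** Mean, median, minimum and maximum are planned, as are listings, individual profile plots and the percentage below 0.2 ng/mL at selected visits (SAP 10.4). A recorded zero would show as the minimum. This stands too, except that nothing says a woman who never reaches 0.2 ng/mL is recorded as zero and not as missing.
- **Evidence that zeros occur.** A reader might infer from "All subjects, except 1 in the undiluted TV-46046 group, had serum MPA levels greater than 0.20 ng/mL 24 hours after treatment initiation" that one woman never reached the threshold. The sentence speaks only of 24 hours; she may have passed it later.
- **Direction of the error.** A reader might infer that the low-dose arm will look longer-acting than it is. That requires zeros to be left out, which the documents do not say. A GM of zero or undefined would be conspicuous, not misleading. The table shells are in a separate document and SAP 10.8 is redacted, so handling there cannot be checked.
- **Distortion by short times.** A reader might also infer that short non-zero times routinely pull the GM far down. An arm with 14 women at 130 days and one at 1 day has GM exp[(14 × ln 130 + ln 1)/15] = 94 days, against 130 if that woman is at 0 and left out. But with immediate peak and exponential decline, 1 day above 0.2 ng/mL at a half-life of 82.87 days needs a peak of 0.2 × 2^(1/82.87) = 0.2017 ng/mL, within 1% of the threshold. That same simple model puts the GM of positive times about 5% to 15% below their median at CV 30% to 60%, but it implies an AUC of 0.53 × 82.87/ln 2 = 63 days·ng/mL, where the protocol reports 94.56. Adding a plateau at the peak of (94.56 − 63.36)/0.53 = 59 days to match that AUC brings the gap down to about 2% to 5%. The larger figures are not expected magnitudes.

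**Conclusion.** The point holds as a minor defect. The SAP states a primary summary that fails for a value the estimate can take, and no visible text supplies a convention. One zero is enough to leave the arm's GM zero or undefined, or to restrict it to women who reached the threshold.

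The exposure is mainly the 120 mg arm, and its size depends on an unstated between-woman CV and on which earlier peak applies: 0.7% to 45% at 0.53 ng/mL, about 3% or less at 0.97 ng/mL, over CVs of 30% to 60%. Both ranges assume log-normal peaks and read the reported peaks as GMs. The documents do not support saying that a zero has occurred, that zeros will be dropped, or that the primary PK comparisons are affected.

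**What to change.** In SAP 10.5, add this duration to the existing exemption for half-life. Suggested wording: *Time at or above 0.2 ng/mL will be summarised primarily by the median, quartiles, minimum and maximum. Women with an evaluable profile that never reaches 0.2 ng/mL will be included with a value of 0 days, and their number will be reported by treatment group.*

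This costs one or two sentences and one table shell and needs no new data. Only the quartiles, the zero convention and the count are new, since the median and range are already produced. The downside is that this row will carry a different headline statistic from the other PK rows, which a footnote can explain.

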10.6. Treatment Group Comparisons

Comparisons between each dose of TV-46046 and the Depo-subQ reference product will be made based on GM ratios (test/reference) and 90% CIs for GM ratios, for the following exposure parameters: C_{max} , C_{91} , C_{182} , C_{210} , AUC_{0-182} , AUC_{0-210} , $AUC_{0-\infty}$, and trough concentrations (C_{182} for each TV-46046 test group and C_{91} for the Depo-subQ provera 104 reference). Confidence intervals will be computed based on the antilog of corresponding limits for the difference in mean log concentrations (computed assuming a student-t distribution for log-transformed values). The assumptions of log-normality and homogeneity of variance will be assessed by inspection of quantile-to-quantile plots, residuals, and tests of departure from these assumptions. The lead biostatistician will use these results to determine whether either assumption is violated to a degree that alternative methods (e.g. bootstrap resampling) should be employed when reporting CIs for GM ratios.

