CLINICAL STUDY PROTOCOL SYNOPSIS

With Amendment 02

Study: TV46046-WH-10159**Title of Study:** A Randomized, Dose-range Finding Study to Evaluate Pharmacokinetics of Medroxyprogesterone Acetate Following a Single Subcutaneous Administration of TV-46046 in Healthy Women of Reproductive Age**Sponsor:** Teva Branded Pharmaceutical Products R&D, Inc.**Investigational New Drug (IND) Number:** 126249**Name of Test Investigational Medicinal Product (IMP):** depot medroxyprogesterone acetate (DMPA [TV-46046])**Active Substance:** medroxyprogesterone acetate (MPA)**EudraVigilance (EV) code for the IMP:** Not Applicable**Type of Study:** Pharmacokinetic (PK) Study**Phase of Clinical Development:** 1**Number of Investigational Centers Planned:** 3 investigational centers**Countries Planned:** United States of America, Dominican Republic**Planned Study Period:** The study is expected to start in Quarter 04 2020 (first subject screened) and have a duration period of approximately 26 months (through last subject out).**Primary Objective(s):** The primary objective of this study is to evaluate and compare the pharmacokinetic profile of MPA following subcutaneous administration of 3 doses of TV-46046 300 mg/mL (120 mg/0.4mL; 180 mg/0.6mL; 240 mg/0.8mL), and 104 mg/0.65 mL of Depo-subQ Provera in healthy female subjects.**Secondary Objective(s):** The secondary objectives of the study are to evaluate and compare the safety, local tolerability, and acceptability of a subcutaneous injection of 3 doses of TV-46046 300 mg/mL (120 mg/0.4mL; 180 mg/0.6mL; 240 mg/0.8mL) and 104 mg/0.65 mL of Depo-subQ Provera in healthy female subjects.**General Study Design and Methodology:** This is a randomized, partially-blinded dose-range finding study to evaluate and compare the pharmacokinetics of MPA, safety, local tolerability, and acceptability of the single subcutaneous administration of 3 doses of TV-46046 300 mg/mL (120 mg/0.4 mL, 180 mg/0.6 mL or 240 mg/0.8 mL), and 104 mg/0.65 mL of Depo-subQ Provera in healthy female subjects of reproductive age. The ultimate goal is to select for further investigation a dose of TV-46046 that is both safe and well tolerated, and has a PK profile consistent with contraceptive protection when injected subcutaneously every 6 months.

Study participation will consist of a screening period (approximately 1.5 months, or 6 weeks), treatment initiation (Day 0) and follow-up (up to 18 months or 78 weeks).

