9.2. Method of Randomization and Blinding

This is a randomized, partially-blinded study. Approximately 60 subjects will be randomized in a 1:1:1:1 ratio to the 4 treatment groups, stratified by site. The randomization sequence will be developed by an FHI 360 Randomization Statistician not otherwise involved in the study using a validated program written in SAS®.

FHI 360 and sponsor project team members involved in assessment of adverse events, data analysis or results interpretation will be blinded to treatment assignment until the planned interim analysis, after which only site staff performing subject interviews and assessing safety outcomes will remain blinded.

A description of emergency unblinding procedures will be described in the study pharmacy manual.

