2.2. Randomization, Allocation Concealment, and Blinding

Subjects will be randomized in a 1:1:1:1 allocation ratio to one of the 3 TV-46046 test groups or the Depo-subQ 104 reference group, using a permuted block design stratified by investigational center. The randomization sequence will be developed by an FHI 360 programmer not otherwise involved in the study using a validated SAS/STAT® program (version 9.4). Randomized subjects who discontinue early will not be replaced. Additional details (including block sizes) are maintained in a separate document.

Allocation will be concealed using opaque, sequentially numbered randomization envelopes provided to each investigational center. Trained staff will open the next available envelope, and allocate the next treatment assignment, only after a subject has completed all other baseline procedures and is determined to be eligible for treatment. Randomization envelopes will be

¹ The study protocol defines day of treatment initiation as Day 0. Noting that the day of treatment initiation is defined as Day 1 in CDISC, protocol Day X will be mapped to treatment Day X+1 when creating ADaM data.

Statistical Analysis Plan Version 5.0

Pharmacokinetics Study–Healthy Subjects

Study TV46046-WH-10159

maintained in a secure location at each center, with access limited to authorized personnel per center-specific study procedures.

The study will only be partially blinded due to differences in appearance of the investigational products. Investigational center staff preparing and administering injections will not be blinded but will be trained to shield the syringe from view of the subject. FHI 360 and sponsor study team members involved in assessment of adverse events, data analysis, and results interpretation will be blinded to treatment assignment until the first interim analysis, after which time only investigational center staff assessing safety outcomes or performing subject interviews will remain blinded. Lab personnel performing MPA testing will remain blinded throughout the study. Emergency unblinding procedures for medical reasons are described in the study Pharmacy Manual and Safety Management Plan. Any instances of unscheduled unblinding will be described in the CSR.

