5.3. Demographic and Baseline Characteristics

Summary statistics appropriate for the measurement scale will be used to describe baseline data. Continuous variables may also be described using categorical levels based on previous experience with similar studies. Baseline data will be presented for the Safety Analysis Set and the Pharmacokinetic Analysis Set (the later only if any subjects are excluded from the Safety Set). Summaries will be provided by treatment group within each investigational center and pooled across centers and treatment groups. No statistical tests will be performed to compare baseline characteristics between treatment groups. [REDACTED]

[REDACTED]

[REDACTED]

[REDACTED]

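### Randomization is stratified by center, but the visible GM-ratio confidence intervals ignore center and will be wider than needed if center affects MPA exposure

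*SAP*

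**What the plan says.** Both documents stratify the randomization by center. Protocol 9.2 allocates subjects in a "1:1:1:1 ratio to the 4 treatment groups, stratified by site", and SAP 2.2 does so "using a permuted block design stratified by investigational center". The protocol synopsis plans "3 investigational centers" across two countries.

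SAP 10.6 compares each TV-46046 dose with Depo-subQ Provera 104 through GM ratios and 90% CIs for eight exposure measures. One of these is the trough ratio (C182 on test against C91 on reference). The method is stated in one sentence: "Confidence intervals will be computed based on the antilog of corresponding limits for the difference in mean log concentrations", with a student-t distribution for the logged values. No covariate is named. A fallback such as the bootstrap is allowed, but only if a distributional assumption fails: "The assumptions of log-normality and homogeneity of variance will be assessed by inspection of quantile-to-quantile plots" and by related checks.

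SAP 10.7 lists two sensitivity analyses, a repeat on the Safety Set and a repeat with imputed C91, C182 or C210. Neither involves center.

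Center does appear in descriptive output. Disposition is tabulated by site (SAP 5.2), and for baseline data "Summaries will be provided by treatment group within each investigational center and pooled across centers and treatment groups". Protocol 9.7 foresees exploratory mixed-effects modeling of subject characteristics such as BMI, but does not name center or link that work to the GM-ratio intervals.

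**The concern.** Blocking within center makes the arms nearly alike in center mix, so a center effect shared by both arms largely cancels from the difference in mean logs. A two-sample t standard error is built from the total within-arm spread, which still contains the between-center part. The interval therefore overstates the uncertainty of the comparison, and its actual coverage exceeds the nominal 90%.

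What is at stake is precision for dose selection. There are about 15 subjects per arm and no hypothesis tests, so the interval is the main visible statement of how well each comparison is known. Protocol 1.4.2 bases the dose range partly on a 6-month trough comparable in geometric mean to the reference product's 3-month trough. The C182/C91 ratio in SAP 10.6 estimates that quantity.

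**Working it through.** **Plan's own figure.** 4 arms × 15 = 60 treated subjects, as SAP 2.5 states. The justification for 15 is redacted, so no SD or precision target can be reproduced.

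**Inputs from the documents.** 15 per arm; 3 centers; 90% CI; log-scale student-t comparison of two arms (SAP 2.5 and 10.6, protocol synopsis). At least 54 evaluable subjects are intended (protocol 9.1), or 54/4 = 13.5 per arm.

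**Assumed, because the documents give no value.** R² is the share of within-arm log-scale variance explained by center: 0, 5, 10, 20 or 30%. Center sizes are also assumed. Center effects are taken as equal in both arms, and variance is pooled over the two arms.

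**Width.** The unadjusted interval has 28 df, with t(0.95, 28) = 1.7011. Adding center uses 2 df, with t(0.95, 26) = 1.7056. With log-scale variance 1:

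- Simple ratio of adjusted to unadjusted width: (1.7056/1.7011) × √(1 − R²).
- With 5 subjects per center per arm and fixed center effects, the unadjusted mean square has expectation [28(1 − R²) + 30R²]/28 = 1 + R²/14. The refined ratio is 1.0026 × √[(1 − R²)/(1 + R²/14)].

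**Coverage of the unadjusted interval.** The true variance of the difference is (1 − R²)(2/15), while the estimate averages (1 + R²/14)(2/15). Coverage is approximately P(|T28| < 1.7011 × √[(1 + R²/14)/(1 − R²)]).

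| Center R² | 0 | 5% | 10% | 20% | 30% |
|---|---|---|---|---|---|
| Width ratio, simple | 1.003 | 0.977 | 0.951 | 0.897 | 0.839 |
| Width ratio, refined | 1.003 | 0.976 | 0.948 | 0.890 | 0.830 |
| Width ratio, simulated (40,000 runs) | 1.002 | 0.975 | 0.946 | 0.888 | 0.829 |
| Unadjusted coverage, approximate | 90.0% | 90.9% | 91.7% | 93.4% | 95.1% |
| Unadjusted coverage, simulated | 90.1% | 90.4% | 91.6% | 93.7% | 95.2% |
| Adjusted coverage, simulated | 90.1% | 89.7% | 89.7% | 90.2% | 90.0% |

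Repeat simulations agreed to within 0.002 in width ratio and 0.7 percentage points in coverage.

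**Other center layouts, simulated over the same R² values.**

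- Unequal centers (9/4/2 against 8/5/2): width ratio 1.005/0.977/0.950/0.893/0.832; unadjusted coverage 90.1/90.7/91.6/93.1/94.6%.
- After losses (5/4/4 against 4/5/5, so 13 against 14 subjects): width ratio 1.008/0.981/0.953/0.895/0.834; unadjusted coverage 89.7/90.5/91.1/92.9/94.5%.
- Adjusted coverage stayed between 89.7% and 90.3% in both.

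**On the ratio scale.** Assume a geometric CV of 50%, so the log-SD is √ln(1.25) = 0.472. The unadjusted limits are the ratio ×/÷ exp(1.7011 × 0.472 × √(2/15)) = 1.341. From the simple formula, the adjusted factor is 1.332 at R² 5%, 1.322 at 10%, 1.301 at 20% and 1.279 at 30%.

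**Unequal variances.** With the reference log-SD 1.25 or 1.5 times the test SD, the two-arm adjusted interval still covered 89.7–90.4%. Pooling variance over all four arms gave 88.0% and 85.8% (balanced, R² = 0), which argues against a four-arm model.

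**Bootstrap fallback.** Percentile resampling within center-by-arm cells covered only 83.8–84.8%. A studentized bootstrap of center-model residuals within arm covered 89.1–90.2%.

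**The case against.** The case for leaving SAP 10.6 alone has several parts.

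- **No error of the harmful kind.** There is no bias, no under-coverage, no hypothesis test and no visible threshold on these intervals. This stands, and it keeps the matter one of precision.
- **The gain may be small.** Nothing in the documents shows that center affects MPA exposure, and common eligibility, injection and sample-handling rules work against it. At R² of 5–10% the factor moves only from 1.341 to about 1.33 or 1.32. This stands.
- **Center effects may differ by arm.** The trough comparison sets different formulations, doses and sampling days against each other. With R² 10% in the test arm, the gain falls from 5.3% to 2.9% if the reference center effect is half as large, and to 1.1% if center matters only on test. With opposite effects, the adjusted interval is 0.6% wider. This reduces the benefit but does not create a material loss.
- **Sparse centers.** A layout of 12/2/0 against 11/2/1 makes the adjusted interval 2.2% wider when center is irrelevant, and one simulation found no gain at R² 10% (ratio 1.001). That result depends on how the center effects are scaled when one center contributes a single subject.
- **Redaction.** SAP 10.8 and part of 5.3 are blacked out and could contain a center analysis. SAP 10.6 also never calls its interval unadjusted; that is read from the description. The point is therefore confined to visible 10.6 and 10.7.
- **Timing.** The interim review, which informs dose selection, may already have taken place. This affects which form of the fix is available.

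Together these points shrink the expected benefit. They leave the downside small, and they do not explain why a factor used to randomize is left out of the analysis.

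**Conclusion.** The concern holds for the visible text, as a conditional precision point. If center is prognostic, the SAP 10.6 intervals are wider than their nominal 90% level requires: about 3–5% at a center share of 5–10%, and 11–17% at 20–30%, where coverage reaches about 94–95%. If center is irrelevant, adjustment costs 0.2% with balanced centers, 0.5–0.8% in the unequal and post-loss layouts, and about 2% in the very sparse one. These sizes rest on assumed center shares and layouts, and on center effects that are similar in the two arms. The change is worth making because it is cheap and matches the design, not because the planned comparison is invalid.

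**What to change.** **If treatment codes are still concealed from the analysis team:** in SAP 10.6, take each GM ratio and 90% CI, including the C182/C91 trough ratio, from a two-arm linear model on the log parameter with treatment and center as fixed effects. Name this as the leading interval. Report the unadjusted ratio and CI beside it so that the table agrees with the group summaries, since under SAP 10.5 "the primary measure of central tendency and dispersion for each pharmacokinetic parameter estimate will be the GM and geometric %CV" (half-life excepted). Do not pool variance over four arms. If the bootstrap fallback is used, keep center in the model and use a studentized bootstrap of its residuals within arm. Leave BMI to the exploratory modeling already planned.

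**If the team is already unblinded:** keep the 10.6 intervals as the leading ones and add the center-adjusted result to 10.7 as supportive. Record the timing in SAP section 12 and the CSR. SAP 2.2 says the team "will be blinded to treatment assignment until the first interim analysis", and section 12 does not make clear whether that unblinding came before Version 5.0, so the sponsor should state which case applies.

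**Cost.** A sentence or two in the SAP, a few lines of code, a section 12 entry and no new data. With balanced centers the adjusted ratio equals the ratio of group GMs. In the unequal and post-loss layouts it departs slightly (assumed geometric CV 50%, center R² 10%): median 1.7–2.1%, 95th percentile 3.9–5.5%. If the adjusted interval leads the final analysis but was not used at the interim, the two sets of intervals will differ in method. If it is added after unblinding, it is not pre-specified and should be labeled so.
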